5.9.3 Vital Signs

Descriptive statistics for vital signs (e.g., systolic and diastolic blood pressure, and pulse rate) and their changes from baseline/Week 0 at each post-baseline/Week 0 visit will be presented for Double-blind Acute and Double-blind Maintenance Phase Safety Analysis Sets, and also for Open-label Acute Phase Safety Analysis Set.

Vital sign values will be considered PCI if they meet either the low or high PCI criteria listed in [Table 3](#). The number and percentage of subjects with PCI post-baseline values will be tabulated. The percentages will be calculated relative to the number of subjects with baseline and at least 1 post-baseline/Week 0 assessment during phase of interest. The numerator is the total number of subjects with at least 1 PCI post-baseline/Week 0 vital sign value during phase of interest.

A supportive listing of subjects with post-baseline/Week 0 PCI values will be provided including the subject number, site, baseline/Week 0, and post-baseline/Week 0 PCI values.

Table 3: Criteria for Potentially Clinically Significant Vital Signs

Vital Sign Parameter	Age (yrs)		
		Lower Limit	Upper Limit
Systolic blood pressure (mmHg)	5 - 6	<89	>125
	7 - 12	<92	>135
	≥13	<100	>140
Diastolic blood pressure (mmHg)	5 - 6	<50	>84
	7 - 12	<55	>90
	≥13	<60	>90
Pulse rate (beats per minute)	5 - 6	<50	>130
	7 - 12	<50	>125
	≥13	<50	>120

5.10 Analysis of Pharmacokinetic Data

Blood samples will be collected for determination of 5-ASA and Ac-5-ASA plasma concentrations, and the plasma samples will be assayed for 5-ASA and Ac-5-ASA using validated analytical methods.

Plasma concentrations reported as BLQ (below the limit of quantification) of the assay will be reported as zero on the data listings, and BLQ concentrations are treated as zero in the calculation of summary statistics.

The plasma concentrations of 5-ASA and Ac-5-ASA will be summarized by treatment and visit using descriptive statistics (number of observations, mean, standard deviation, coefficient of variation, median, Q1, Q3, maximum, and minimum) using the Safety Analysis Set for each study phase.

A population pharmacokinetic model was developed based on the 5-ASA and Ac-5-ASA plasma concentration data (full pharmacokinetic profiles) from SPD476-112. The plasma concentration data from this study (sparse pharmacokinetic sampling) will be pooled with the plasma concentration data from SPD476-112 to update the original population pharmacokinetic analysis. The population pharmacokinetic methods will be described in a separate document from this statistical analysis plan.

6. CHANGES TO ANALYSES SPECIFIED IN THE PROTOCOL

- Changes to the analyses specified in the protocol are as follows: The observed-case sensitivity analysis has been removed from the SAP, since the observed-case analysis would be identical to the complete-case analysis. The model-based imputation method sensitivity analysis has been omitted from the SAP as this study is not powered to detect differences between treatment groups and other sensitivity analysis (LOCF and complete case) intended to examine the robustness of the treatment estimate (under the assumption that the subjects with missing Week 8 or Week 26 results are treatment failures) have been included.
- Statements were added to the SAP to clarify that this is an estimation study intended to provide estimates of clinical response for 2 doses (low and high) across a range of weight groups and not powered to detect differences between treatment groups.
- After agreement with FDA, the sample size for the Double-blind Acute Phase has been reduced to 53 subjects due to difficulties with recruitment.
- Subgroup analyses for the primary endpoint were added to the SAP to explore efficacy by weight group and Week 8 responder status.
- For maintenance phase secondary endpoints, the proportion of subjects who have maintained a clinical and endoscopic response at Week 26, using central reading and using local reading endoscopies, if there are an insufficient number of subjects with central reading endoscopy data, then the CMH test will not be performed. The number and percentage of subjects with clinical and endoscopic response will be presented by treatment arm.
- To conduct psychometric analysis of the DUCS would require more data, and thus will be considered in the future.

7. STATISTICAL/ANALYTIC ISSUES

7.1 Adjustment for Covariates

The analysis of the primary efficacy endpoint for the Double-blind Acute Phase does not include adjustment for covariates.

The analysis of the primary efficacy endpoint for the Double-blind Maintenance Phase includes adjustment for prior response status (entered Maintenance Phase directly, responder at Week 8 in Double-blind Acute Phase, responder at Week 8 in Open-label Acute Phase).

The analysis of the secondary efficacy endpoint, change in DUCS score from baseline to Week 8 for the Double-blind Acute Phase includes adjustment for the baseline DUCS score.

The analysis of the secondary efficacy endpoint, change in DUCS score from Week 0 to Week 26 for the Double-blind Maintenance Phase includes adjustment for the baseline DUCS score and prior response status (entered Maintenance Phase directly, responder at Week 8 in Double-blind Acute Phase, responder at Week 8 in Open-label Acute Phase).

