3.3 Method of Assigning Subjects to Treatment Groups

This study includes 2 double-blind phases with low- and high-dose MMX mesalamine/mesalazine. The actual double-blind treatment given to individual subjects is determined by a randomization schedule stratified by weight group. Randomization will be a 1:1 ratio between low and high doses.

Subject numbers are assigned to all subjects as they consent to take part in the study. Within each site (numbered uniquely within a protocol), the subject number is assigned to subjects according to the sequence of presentation for study participation.

The randomization number represents a unique number corresponding to investigational product allocated to the subject, once eligibility has been determined.

Subjects eligible for either the Double-blind Acute or the Double-blind Maintenance Phase can be re-randomized if they initially failed randomization for the following reasons: incorrect use of IVRS, late or missing central laboratory or endoscopy results, or other reasons of this type as long as they meet inclusion and exclusion criteria. Re-randomization can only take place after consultation with the medical monitor.

Individual subject doses in the Double-blind Acute Phase are automatically assigned by the interactive response technology (IRT) based on subject weight group at the Baseline Visit (Visit 2). If the subject is directly entering the Double-blind Maintenance Phase, individual doses are also automatically assigned by the IRT based on subject weight group at the Baseline Visit (Visit 2).

Individual subject open-label treatment is automatically assigned by the IRT and will be the high dose based on the subject's weight group at Visit 3.2 (Week 8/Withdrawal of the Double-blind Acute Phase).

Individual subject double-blind doses for subjects being re-randomized to the Double-blind Maintenance Phase after completion of treatment at Visit 3.2 (Week 8 of the Double-blind Acute Phase) or Visit 4.2 (Week 8 of the Open-label Acute Phase) are automatically assigned by the IRT based on subject weight group at the time of re-randomization.

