5. STATISTICAL ANALYSIS

5.1 General Methodology

All statistical analyses will be performed using SAS® Version 9.2 or higher (SAS Institute, Cary, North Carolina, USA).

Unless otherwise specified, summary tabulations using the Double-blind Acute Phase and Double-blind Maintenance Phase Safety Analysis Sets will be presented by treatment arm and overall. Summary tabulations using the Open-label Acute Phase Safety Analysis Set will be presented by high-dose only. Summary tabulations using the Overall will be presented by overall only.

For categorical variables, the number and percentage of subjects within each category (with a category for missing data as needed) of the parameter will be presented. For continuous variables, the number of subjects, mean, median, standard deviation (SD), Q1, Q3, minimum, and maximum values will be presented.

This is an estimation study intended to provide estimates of clinical response for 2 doses (low and high) across a range of weight groups and not powered to detect differences between treatment groups. P-values will be presented as descriptive statistics.

All statistical tests will be 2-sided hypothesis tests performed at the 5% level of significance for main effects. All confidence intervals will be 2-sided 95% confidence intervals, unless stated otherwise.

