5.8.1.1 Double-blind Acute Phase

The primary efficacy endpoint for the Double-blind Acute Phase is defined as the proportion of subjects with a clinical response (defined as partial UC-DAI \leq 1 with rectal bleeding=0, stool frequency \leq 1, and PGA=0) at Week 8.

- Subjects with missing data at Week 8 will be assumed not to have had a clinical response. The primary efficacy endpoint will be compared between treatment arms using a continuity corrected chi-squared test on the Double-blind Acute Phase Safety Analysis Set. If any of the expected cell counts are very low (i.e., less than 5), then Fisher's Exact Test will be used as an alternative analysis method.
- The null hypothesis to be tested is that there is no difference in the proportion of subjects with a clinical response at Week 8 between low and high doses of MMX mesalamine/mesalazine.
- The number (n, %) of subjects with a clinical response at Week 8 and the difference between treatment arms, together with the 95% CI (2-sided), and associated p-value will be presented. The odds ratio comparing the two treatments, together with the 95% CI (2-sided) will also be presented.

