7.5 Multiple Comparisons/Multiplicity

This is an estimation study intended to provide estimates of clinical response for 2 doses (low and high) across a range of weight groups and not powered to detect differences between treatment groups. No adjustment for multiplicity will be performed.

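### The acute primary analysis is not stratified by weight group, and the SAP names no method for the 95% CIs printed beside its continuity-corrected p-value

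*SAP*

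**What the plan says.** This point concerns the primary endpoint of the Double-blind Acute Phase only.

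SAP 3.3 says that double-blind treatment "is determined by a randomization schedule stratified by weight group", in a 1:1 ratio, and names no other stratum. SAP 7.1 then says: "The analysis of the primary efficacy endpoint for the Double-blind Acute Phase does not include adjustment for covariates".

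Under SAP 5.8.1.1 the endpoint is "compared between treatment arms using a continuity corrected chi-squared test on the Double-blind Acute Phase Safety Analysis Set", with Fisher's exact test if any expected count is below 5. Protocol 9.8.1.1 specifies the same chi-squared test. The same SAP section presents the number of responders "and the difference between treatment arms, together with the 95% CI (2-sided), and associated p-value will be presented". It adds: "The odds ratio comparing the two treatments, together with the 95% CI (2-sided) will also be presented". Neither this section nor SAP 5.1 gives a method for these two intervals.

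SAP 5.1 contains both "All statistical tests will be 2-sided hypothesis tests performed at the 5% level of significance for main effects" and "P-values will be presented as descriptive statistics". SAP 7.5 describes an estimation study "intended to provide estimates of clinical response for 2 doses (low and high) across a range of weight groups".

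Weight appears elsewhere. SAP 7.6.1 and Table 14.2.1.2.1 give response by arm and weight group, and SAP Section 6 records that addition. SAP 7.7.1 plans a logistic model on mg/kg dose, sex and age.

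**The concern.** There are two separate gaps.

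First, a continuity-corrected p-value does not correspond to the usual CIs for a difference or an odds ratio, which carry no correction. With no CI method named, the primary table can show p>0.05 beside a 95% CI that excludes no difference. In an estimation study the CI is the main result, so its method should be fixed before unblinding.

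Second, the comparison ignores the factor by which subjects were randomised. When a stratification factor is related to outcome, an unstratified variance formula does not credit the balance that the allocation created, and the printed CI is wider than it need be. No planned output fills this gap. The weight-group table gives response within groups and no pooled arm difference. The logistic model has no weight-group term and replaces arm by mg/kg dose, so it does not give an arm difference either.

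**Working it through.** **Inputs.** N=53 is from SAP 3.5. With 1:1 allocation it is taken as 26 low v 27 high, which is an assumption. The two-sided 5% level and 95% CIs are from SAP 5.1, and the test rule is from SAP 5.8.1.1. The documents give no response rates, so those below are assumed. They also give no power or precision figure to reproduce.

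**Step 1: one table, 8/26 v 16/27.** There are 24 responders and 29 non-responders. The smallest expected count is 26×24/53 = 11.8, so the chi-squared test applies.

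- Cross-product difference: |8×11 − 18×16| = 200.
- Corrected chi-squared: 53×(200 − 26.5)²/(26×27×24×29) = 1,595,419/488,592 = 3.27, **p=0.071**. (Uncorrected: 53×200²/488,592 = 4.34, p=0.037.)
- Difference: 0.593 − 0.308 = 0.285, SE = √(0.308×0.692/26 + 0.593×0.407/27) = 0.131.
- Wald CI: 28.5 ± 1.96×13.1 = 2.8 to 54.1 points. Newcombe CI: **1.8 to 50.1 points**.
- Odds ratio: (16×18)/(8×11) = 3.27, SE of its log = √(1/8+1/18+1/16+1/11) = 0.578, CI 1.05 to 10.16.
- Continuity-corrected Wald CI: widened on each side by (1/26 + 1/27)/2 = 3.8 points, giving −0.9 to 57.9.

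All three uncorrected CIs exclude no difference while p is above 0.05.

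**Step 2: how often.** All 27×28 = 756 possible tables were enumerated and weighted by binomial probabilities. Entries are the percentage of trials with p>=0.05 under the SAP rule and a CI that excludes no difference.

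| True rates, low v high | Wald | Newcombe | Log odds ratio | Corrected Wald |
|---|---|---|---|---|
| 30 v 30% | 3.6 | 2.6 | 1.9 | 0.6 |
| 30 v 50% | 12.3 | 10.2 | 9.1 | 3.3 |
| 40 v 60% | 9.7 | 9.4 | 9.4 | 0.5 |
| 30 v 60% | 12.5 | 11.6 | 11.2 | 2.0 |
| 40 v 70% | 11.4 | 11.3 | 11.3 | 0.2 |

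At equal rates of 20-60% the SAP rule gives p<0.05 in 2.5-2.7% of trials, against the stated 5%. The test is conservative.

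A continuity-corrected CI removes most of the disagreement but not all. For 6/26 v 14/27, p=0.0605 and the corrected Wald CI is 0.2 to 57.4 points.

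**Step 3: stratification.** The SAP Table 1 minima (2/12/18/36, total 68) were scaled by 53/68 to 2/9/14/28, and the lowest two groups pooled to give 11/14/28, split 5/7/14 v 6/7/14. This is an assumption. The stratified estimate is the Mantel-Haenszel risk difference, Σw_k d_k/Σw_k with w_k = n_1k n_2k/(n_1k + n_2k), with Sato variance. Simulation with no dose effect gives:

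| Response by weight stratum | SD of estimate, crude v stratified | Mean 95% half-width (points), crude v stratified | Crude CI coverage |
|---|---|---|---|
| Flat | 0.135 v 0.135 | 25.9 v 25.9 | 0.943 |
| 25/40/60% | 0.132 v 0.132 | 26.4 v 25.3 | 0.955 |
| 15/40/70% | 0.123 v 0.123 | 26.5 v 23.6 | 0.967 |

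Coverage of the stratified CI is 0.936-0.942 across scenarios. The SDs are equal because stratified allocation has already balanced weight. Only the printed width changes. In the steepest case the true sampling spread is 1.96×0.123 = 24.1 points: the crude CI overstates it (26.5) and the stratified CI slightly understates it (23.6).

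**The case against.** The strongest reply is that no decision rests on this p-value. SAP 5.1 makes p-values descriptive, and SAP 3.5 and 7.5 call this an estimation study, so the plan already points the reader to the estimate and CI. That stands, and it rules out a stronger reading. A reader might infer that the mismatch inflates error or undermines the test. It does not: the test is conservative and nothing formal depends on it.

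A reader might also infer that stratifying would sharpen the estimate. Step 3 shows that it would not. The unstratified CI is valid and at worst conservative, the documents give no evidence that weight is prognostic, and the strata and gradients are assumed. So the stratified estimate belongs in a supportive role.

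Nor do the documents support saying that the SAP disregards weight. It has a weight-group table and an mg/kg model. What is missing is a pooled arm comparison stratified by weight group.

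Finally, the CI method may be fixed elsewhere. SAP 1.1 places table specifications in a separate document, and SAP 8.1 refers to a reporting standard. If these prescribe a continuity-corrected Wald CI, the disagreement in Step 2 for the difference is already only 0.2-3.3%. What survives is that the SAP itself leaves the method of its main result unstated and omits the randomisation stratum from the comparison.

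**Conclusion.** The point holds in a limited form, for the acute primary endpoint only. If the CIs are the usual uncorrected ones, the primary table would carry a p-value and a CI that disagree in about 2-4% of trials with no effect (equal rates of 30-50%) and in 9-13% at true differences of 20-30 points. This is an inconsistency of reporting.

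The unstratified CI is wider than it need be only if weight is prognostic: by about 1 point of half-width under a moderate assumed gradient (26.4 v 25.3) and about 3 points under a strong one (26.5 v 23.6). Otherwise nothing changes.

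The disagreement figures rest on the 26/27 split, the assumed response rates and uncorrected CIs. The width figures rest also on the assumed strata. Both changes are worth making because they cost little and the downsides are small.

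**What to change.** 1. In SAP 5.8.1.1, add a supportive estimate stratified by weight group: Mantel-Haenszel risk difference (Sato variance) and common odds ratio (Robins-Breslow-Greenland variance), each with a 95% CI. Pool the two lowest weight groups (18 to 35 kg). Give it no p-value of its own.
2. In the same section, keep the Protocol's test and name the CI methods for the difference and the odds ratio. State that the estimate and CI are the primary result and that the corrected p-value is descriptive. Then either pair that p-value with a continuity-corrected CI for the difference, or state that the p-value is more conservative than the CIs. The odds-ratio CI needs that statement in either case, because the corrected CI covers only the difference.
3. Do not print a second, uncorrected p-value. At differences of 20-30 points the two p-values would fall on opposite sides of 0.05 in 9-12% of trials, which recreates the conflict.
4. Record both additions in SAP Section 6.

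The cost is a few sentences and a few lines of code, since weight group is already held in the randomisation system. The downsides are pooling of sparse strata, slight under-coverage of the Mantel-Haenszel CI (about 0.94) and, if chosen, a corrected CI that is 3.8 points wider on each side and over-covers (0.968-0.972).

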4.1 Inclusion Criteria

The subject will not be considered eligible for the study without meeting all of the criteria below.

General:

1. Ability to voluntarily provide written, signed, and dated (personally or via a legally authorized representative [LAR]) informed consent or assent as applicable to participate in the study.
2. Subject's parent/LAR demonstrates an understanding, ability, and willingness to fully comply with study procedures and restrictions.
3. Male and female children and adolescents aged 5-17 years, inclusive, at the Baseline Visit (Visit 2).
4. Body weight 18-90 kg at the Screening Visit (Visit 1) and the Baseline Visit (Visit 2).
5. Male, or non-pregnant, non-lactating female who agrees to comply with any applicable contraceptive requirements of the protocol or females of non-childbearing potential.
6. Diagnosed with mild to moderate UC, established by sigmoidoscopy or colonoscopy with compatible histology. Screened subjects may also have an unconfirmed diagnosis of mild to moderate UC; however, the diagnosis of mild to moderate UC must have been established by sigmoidoscopy or colonoscopy with compatible histology prior to the Baseline Visit (Visit 2).

7. Subject is able to swallow the investigational product whole.

Double-blind Acute Phase:

8. Partial UC-DAI score ≥ 2 (with a combined rectal bleeding **and** stool frequency score ≥ 1 **and** PGA=1 or 2) **and** with mucosal appearance (endoscopy score)=2 or 3 at the Baseline Visit (Visit 2), for which 5-ASA would be used as part of normal treatment.
9. If the subject is on 5-ASA treatment prior to study entry, then the dose must be stable. Stable therapy is defined as no change in dose, or no initiation of 5-ASA, from the onset of the current acute flare through discontinuation of therapy (required at the Baseline Visit; Visit 2). See exclusion criterion 28 for an additional 5-ASA dose-related requirement.

Double-blind Maintenance Phase:

10. Partial UC-DAI ≤ 1 (with rectal bleeding=0 **and** stool frequency ≤ 1 **and** PGA=0) **and** with mucosal appearance (endoscopy score)=0 or 1 at the Baseline Visit (Visit 2).

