5.8.2.1 Double-blind Acute Phase

- The proportion of subjects with a clinical and endoscopic response at Week 8, defined as UC-DAI ≤ 2 with rectal bleeding=0 and stool frequency ≤ 1 and PGA=0, and with mucosal healing (endoscopy score ≤ 1) based on central reading. In addition, there must be at least a 1-point reduction in endoscopy score from baseline. This endpoint will be compared between treatment arms using a continuity corrected chi-squared test. If any of the expected cell counts are very low (i.e., less than 5), then Fisher's Exact Test will be used as an alternative analysis method. Subjects with missing data at Week 8 will be assumed not to have had a clinical response. Subjects who completed week 8 but who did not have central reading endoscopies at both baseline and week 8 will be excluded.
- The proportion of subjects with a clinical and endoscopic response at Week 8, defined as UC-DAI ≤ 2 with rectal bleeding=0 and stool frequency ≤ 1 and PGA=0, and with mucosal healing (endoscopy score ≤ 1) based on local reading. In addition, there must be at least a 1-point reduction in endoscopy score from baseline. This endpoint will be compared between treatment arms using a continuity corrected chi-squared test. If any of the expected cell counts are very low (i.e., less than 5), then Fisher's Exact Test will be used as an alternative analysis method. Subjects with missing data at Week 8 will be assumed to be treatment failures. Subjects with missing data at Week 8 will be assumed not to have had a clinical response. Subjects who completed week 8 but who did not have local reading endoscopies at both baseline and week 8 will be excluded.
- The change in the DUCS score from baseline to Week 8 of the Double-blind Acute Phase. This endpoint will be compared between treatment arms using an analysis of covariance (ANCOVA), including treatment arm as a factor and the baseline DUCS score as a covariate in the model.
- The percentage of subjects with an improvement (change of ≥ 20 points) in PUCAI score from baseline to Week 8 of the Double-blind Acute Phase. This endpoint will be compared between treatment arms using a continuity corrected chi-squared test. If any of the expected cell counts are very low (i.e., less than 5), then Fisher's Exact Test will be used as an alternative analysis method. Subjects with missing data at Week 8 will be assumed not to have had a clinical response.

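### The acute primary analysis leaves out baseline partial UC-DAI, which is known for every randomised child; the crude estimate is valid, but a pre-specified adjusted risk difference would probably be modestly more precise.

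*SAP*

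**What the plan says.** - **Analysis.** SAP 7.1 says "The analysis of the primary efficacy endpoint for the Double-blind Acute Phase does not include adjustment for covariates". SAP 5.8.1.1 says the endpoint is "compared between treatment arms using a continuity corrected chi-squared test on the Double-blind Acute Phase Safety Analysis Set", with Fisher's exact test if any expected count is below 5. It reports the crude difference and the odds ratio, each with a 95% CI. Protocol 9.8.1.1 names the same chi-squared test.
- **Endpoint.** Week 8 response requires rectal bleeding 0, stool frequency at most 1 and PGA 0. A partial UC-DAI total of at most 1 then follows automatically. A missing Week 8 result counts as non-response.
- **Baseline score.** Inclusion criterion 8 (Protocol 4.1) requires a partial UC-DAI of at least 2, "with a combined rectal bleeding" and stool frequency score of at least 1, and PGA 1 or 2. Protocol 7.2.1.1 requires at least one diary score for each symptom before randomisation.
- **Allocation and size.** SAP 3.3 makes treatment "determined by a randomization schedule stratified by weight group", in a 1:1 ratio. Baseline severity is not a stratification factor. SAP section 6 says: "After agreement with FDA, the sample size for the Double-blind Acute Phase has been reduced to 53 subjects due to difficulties with recruitment".
- **Other analyses.** The acute logistic sensitivity model (SAP 7.7.1) uses dose in mg/kg, sex and age. The acute subgroup analysis (SAP 7.6.1) uses weight group. Neither includes baseline severity. The acute DUCS comparison (SAP 5.8.2.1) does adjust for its own baseline, "including treatment arm as a factor and the baseline DUCS score as a covariate in the model".

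**The concern.** The endpoint is built from the same three components that are scored at entry, and children start at very different distances from meeting it. A child entering at 2 through PGA 1 and stool frequency 1 has only to reach PGA 0, a fall of 1 point. A child entering at 8 has to fall 7 points. Baseline severity is therefore a plausible predictor of response. It is already collected, and nothing in the plan uses it when estimating the dose difference.

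The study is presented as estimating response at two doses, with p-values descriptive only. The width of the interval for the dose difference is therefore the quantity that matters, and with about 26 children per arm it will be wide. Using a collected predictor is one of the few ways to narrow it without more patients.

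**Working it through.** **The plan's own figure.** There is nothing to reproduce. The 53 rests on recruitment and agreement with FDA; the documents give no response rate, effect size, power or precision target for it.

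**Baseline range (from the documents).** The minimum is 2. The maximum is bleeding 3 + stool frequency 3 + PGA 2 = 8. This is the permitted range, not an observed distribution.

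**Crude precision.** Assumed response rates are 35% and 60%, with 53/2 = 26.5 per arm.

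- SE = √[(0.35×0.65 + 0.60×0.40)/26.5] = √(0.4675/26.5) = 0.1328
- Half-width = 1.96 × 0.1328 = 26.0 percentage points

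With a common response rate and arms of 26 and 27, 1.96 × √[p(1−p)(1/26 + 1/27)] gives 24.7, 26.4 and 26.9 points at 30%, 40% and 50%.

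**Precision after adjustment (large-sample formula).** The half-width is multiplied by √(1−ρ²), where ρ is the assumed correlation between baseline score and response. The equivalent sample size is 53/(1−ρ²).

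| ρ | Half-width (points) | Narrower by | Equivalent N |
|---|---|---|---|
| 0 | 26.0 | 0% | 53 |
| 0.3 | 24.8 | 5% | 58 |
| 0.4 | 23.9 | 8% | 63 |
| 0.5 | 22.5 | 13% | 71 |

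**What these correlations imply.** Assume baseline scores roughly normal with mean 5 and SD 1.5, cut to 2–8, and 40% response overall. Odds ratios for response of 0.82, 0.67, 0.55 and 0.45 per baseline point then give ρ of about 0.13, 0.25, 0.35 and 0.44. A ρ of about 0.5 needs an odds ratio near 0.37 per point, meaning about 80% response at a score of 3 and under 10% at 7. That is optimistic.

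**Simulation.** Each setting used 4,000 trials of 53 children with no dose effect. The crude difference was compared with a standardised risk difference from a logistic model with arm and baseline score. The change in interval width is the square root of the variance ratio.

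| Odds ratio per point | Variance ratio, adjusted/crude | Interval width |
|---|---|---|
| 1.00 (uninformative) | 1.018 | about 1% wider |
| 0.82 | 0.995 | under 1% narrower |
| 0.67 | 0.934 | about 3% narrower |
| 0.55 | 0.892 | about 6% narrower |
| 0.45 | 0.832 | about 9% narrower |

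At an odds ratio of 0.45 (ρ = 0.44) the formula gives 1 − √(1 − 0.193) = 10%. The supported range is therefore about 0–10% narrower, or about 1% wider if baseline carries no information. Bias was close to zero for both estimators in every setting.

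**Chance imbalance.** The standardised baseline difference between arms has SD √(1/26 + 1/27) = 0.27, so it exceeds 0.25 SD in about 36% of randomisations and 0.5 SD in about 7%. Under the assumed distribution, a difference of 0.5 baseline points moves the crude dose difference by about 5 points (odds ratio 0.67) to 8 points (odds ratio 0.45).

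**The case against.** The strongest defence is that the planned analysis is valid, explicit and fixed in the protocol. Several parts of it stand.

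- **A reader might infer that the crude result is biased by severity imbalance. It is not.** Randomisation makes the crude difference unbiased, and its interval already allows for chance imbalance on average. Imbalance would also be visible, because SAP 5.8.3.1 summarises partial UC-DAI by visit and arm. What remains is lost precision and the reading of this one allocation.
- **Baseline total is an imperfect proxy.** Response is a rule on components. A child entering at 2 through PGA 1 and bleeding 1 must fall 2 points, whereas one with PGA 1 and stool frequency 1 need fall only 1. This argues for modest expectations.
- **A reader might present the gain as power, from 47% to 58%. The documents do not support that.** P-values are descriptive. The 47% is an uncorrected normal approximation; exact enumeration of the planned test (26 versus 27, 35% versus 60%) gives about 35%. The 58% also needs the optimistic ρ of 0.5.
- **A reader might see an inconsistency with DUCS.** That is weak. DUCS is a continuous change score, for which ANCOVA is routine, and all the binary acute endpoints share the same unadjusted test.
- **The change is not purely SAP wording.** Because the protocol names the test, a new main estimate has to be declared as a change.

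None of this supplies the adjustment elsewhere or removes the likely gain in precision.

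**Conclusion.** The point holds as one of efficiency, not validity. The acute primary comparison makes no use of a plausibly prognostic score that is available for every randomised child, in a phase of 53 whose stated purpose is estimation.

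The likely benefit is modest: an interval about 0–10% narrower around a half-width of about 26 points, with 24.8 points at ρ = 0.3 as a reasonable central case. The 22.5 points at ρ = 0.5 is an optimistic bound and should not lead. If baseline is uninformative the interval is about 1% wider. These figures rest on assumed response rates, an assumed baseline distribution and an assumed prognostic strength, none of which the documents give. The gain applies to a standardised (marginal) risk difference. A conditional odds ratio is a different quantity, and its standard error need not shrink.

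Adjustment will not turn 53 children into a precise dose comparison. It is still worth pre-specifying, because it needs no new data and would be post hoc if added after unblinding.

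**What to change.** Before unblinding, amend SAP 5.8.1.1 and 7.1, and list the change in SAP section 6 as a departure from the protocol:

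1. Make the main estimate of the acute dose difference a standardised (marginal) risk difference with 95% CI, from a logistic model with treatment and continuous baseline partial UC-DAI.
2. Add weight group, the stratification factor, if numbers allow. State in advance how that will be decided.
3. Name the fallback if the model does not converge, for example Firth's penalised likelihood. Name the interval method and check its coverage at about 26 per arm.
4. Keep the protocol's continuity-corrected chi-squared/Fisher test and the crude difference alongside.

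The non-response rule for missing Week 8 data is unchanged, so no child is lost from the model. The cost is SAP text, a few lines of code, a small coverage check and a slightly more complex primary table. The return is small if baseline proves weakly prognostic.
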